Because the BCT process is interactive and iterative, recording and transcribing sessions is often impractical. Instead, field notes will be taken by our team in English and/or Spanish during each session and shared during weekly meetings of the project team. Reminder materials tailored through BCT and proposed protocols for the intervention will be reviewed by members of the IMW HPV Vaccination Coalition and tested during study Aim 2. Following BCT, we will finalize our trial protocol, including procedures for the Auto and the Auto-Plus arms of the intervention, and will finalize methods for data coordination, management, and ongoing monitoring. Because our goal is to craft materials and messages that are motivating for English- and Spanish-speakers, we do not anticipate directly translating materials from English to Spanish. Instead, we rely on BCT and native speakers to craft messages from the ground up; this approach was successful in prior research. We aim for a broad scale-up, all English and Spanish materials will be reviewed by the Sea Mar marketing and communications office for appropriateness and equivalency. C.4.b. Update Data Sources and Codes: In preparation for the RCT, we will define automated codes to manage interventions so that P/Cs of vaccine eligible C/As, who receive initial HPV vaccination, are prompted to receive follow-up vaccine on time. [name], a community clinic EHR data expert, will lead this work.

Inclusion and Exclusion Criteria and Data Sources: Working with clinic staff, our research team will use patient-level inclusion and exclusion criteria based on current HPV vaccine guidelines to determine P/C participant eligibility. These criteria will consider previous HPV vaccination history, clinic visits (as a proxy for patient enrollment), clinical conditions that influence CDC HPV vaccine recommendations (e.g., pregnancy), age (11-17), and other factors. For this study, language will also be a criterion, as we plan to conduct the intervention in English and Spanish. We anticipate that EHR systems at our 4 clinics will likely provide complete information on vaccination status for HPV and other vaccines (e.g., Tdap, meningococcal). The Washington State Department of Health maintains accurate, up-to-date information on vaccination status in the WA-IIS, and

patient-level immunization data are already routinely provided to Sea Mar through a health information exchange. As part of Aim 1, we will perform sensitivity analysis, cross tabulation, and targeted chart audits (of up to 100 charts from each clinic) to assess the agreement between HPV vaccine events found in the EHR and in the state-level vaccine registries, recognizing that previous studies have reported agreement ranging from 96% to 99%. Epic offers existing tools for documenting external procedures and discrete code-based fields for categorizing laboratory events and needed follow-up. We will provide support and training to enter these data within our clinics' EHR, to assure complete data when possible.

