## C. APPROACH

C.1. Project Overview: This two-stage study was designed in collaboration with Sea Mar Community Health Centers, an active member of [name] IMW HPV Vaccination Coalition. 65 The proposed project optimally aligns with the expertise of the study team and leverages our clinic partner's commitment to improving HPV vaccination and reducing disparities in HPV-related cancer incidence and mortality. Our study will test automated and live reminders for HPV vaccination (Figure 4). In Phase I (Years 1-2), we will refine intervention components and messages to increase HPV vaccination among rural C/A. We will use a validated patient-engaged approach for P/Cs, BCT, with separate sessions conducted in English and Spanish. In Phase II, we will conduct a P/C randomized controlled trial (RCT) that tests automated strategies (e.g., automated phone calls,

[figure not shown]

Figure 4. PREVENT Study Design.

EHR = electronic health records; RCT = randomized controlled trial; HPV = human papillomavirus

text messages) and combined automated and interactive live strategies to prompt P/Cs of vaccine-eligible C/A to complete the next dose of the HPV vaccine (i.e. first, second, or third dose depending on age of C/A). The individual-RCT will include P/Cs of 1038 vaccine-eligible patients at 4 rural clinics in Washington (Rural-Urban Continuum Codes of 3-9). This trial could significantly reduce HPV-associated cancer disparities and can be sustained long-term.

C.2. Research Team and Preliminary Data: Our multidisciplinary team includes investigators with a record of developing and testing multiple cancer prevention interventions; analysts with years of experience designing registries and reminder and recall systems; implementation scientists; and qualitative researchers. [name] will lead this project in partnership with [name] and [name], Medical Director at Sea Mar,

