rural Utah, Colorado, Nevada, Montana, and Arizona (N=140 participants; 3P30 CA042014-2958). Focus groups assessed system-level barriers and needed adaptations for implementing evidence-based HPV vaccination strategies in rural primary care clinics (**Table 1**).84 The findings underscore P/Cs' uncertainty about which vaccines to get and providers' and stakeholders' desire for systems to remind P/Cs to obtain the vaccine. [name] hosts monthly video-call meetings with partners (**Letters of support**).65,82

Table 2. Selected Sea Mar Community Health Center Clinics\*

Sea Mar Clinic Location	N patients (2019)	% Rural	% His- panic	N patients ages 11-17 years	Among Patients Ages 11-12 Yrs.*		Among Patients Ages 13-17 Yrs.*	
					% HPV vac. Initiat.	% HPV vac. complet.	% HPV vaccine initiat.	% HPV vaccine complet.
Ocean								
Shores	2971	40.1	5.6	158	36.7	2.6	45.5	25.6
Aberdeen	3941	40.1	14.9	241	45.4	8.5	62.1	44.8
Elma	982	40.1	21.8	73	53.3	16.3	74.7	67.7
Yelm	4088	29.0	13.0	566	48.3	18.2	58.5	44.3

\*Estimated 5% decline in HPV vaccination rates shown due to COVID-19 pandemic challenges

[name], an epidemiologist, is bilingual in English and Spanish and a national leader in practice-based cancer prevention research in safety net clinics. [name] and her team have established formal collaborations

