Consistent with the desire of clinic staff to integrate this project into their standard workflows, we will use automated codes to manage interventions so that eligible patients get initial HPV vaccines on time and P/C are prompted to repeat vaccination, as recommended. Our EHR tools rely on Reporting Workbench, a population management tool in Epic which will be customized to include tools needed for tracking completion of HPV vaccination at the 4 intervention clinics. The registry will list patients' HPV vaccination history as well as key demographic variables for the intervention (e.g., name, address, preferred language). We will select a cohort of approximately 1,038 P/C of patients from the 4 clinics, randomized to intervention arms (UC, Auto, and Auto-Plus) stratified by clinic, sex, and language preference (English, Spanish, other) to ensure a nearly balanced distribution of clinic, sex, and language preference among study arms. The registry will generate 2 real-time reports: 1] HPV vaccination outcomes (i.e., date of vaccination events, and whether the event represents series initiation, second dose, and/or series completion); and 2] PREVENT intervention activities (i.e., date of

Table 3: Schedules of Measures (part.=participants; T=time, Y=year; M=month)								
Variable	Data source	How measured	Proctor/ RE- AIM domain	Т				
Aim 1: Bootcamp Translation (BCT)								
Rural parent-/ caregiver- & provider-driven adaptations/ program acceptance	Parents / providers	Notes from BCT sessions	Adaptations, Acceptance	Y 1				
Aim 2: PREVENT Randomized 0	Controlled Trial (I							
Reach of RCT – primary outcome (next needed HPV vaccine dose)	EHR; vendor logs	N part. receive program/ N anticipated, reasons	Reach	6 m				
Reach of RCT – secondary outcome (completion of HPV vaccine series)	EHR; vendor logs	N part. receive program/ N anticipated, reasons	Reach	6 m				
Effectiveness of RCT – primary outcome	EHR	N C/A complete next HPV vaccine dose/ N anticipated	Effectiveness	6 m				
Effectiveness of RCT – secondary outcome	EHR	N C/A complete all doses of HPV vaccine  / N anticipated	Effectiveness	13 m				
Aim 3: Tertiary and Qualitative	Outcomes							
Moderators (e.g., sex of parent, sex of child, age, ethnicity, etc.)	EHR data	Effectiveness of intervention by presence of moderator	Equity	6 m				
Parent/caregiver reactions	Interviews	Coded transcripts	Acceptance	Y 3				

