Program Effectiveness: We will assess intervention effectiveness for each of the three study arms, calculated as the proportion of eligible children/adolescents who received any HPV vaccine within 6 months and 13 months (series completion by one year) of randomization. We will assess the proportion of C/A who initiated HPV vaccination, those who received the next needed dose and the percent who completed the series.

Study Design: We propose a 3-arm RCT to compare rates of completing the next step in the HPV vaccination series at 6 months and completing the HPV vaccination series at 13 months between Auto, Auto-Plus, and UC arms. P/C of C/A who have not completed the HPV vaccination series will be randomized 1:1:1 to study arms, with separate randomizations within each clinic (Ocean Shores, Aberdeen, Elma, or Yelm) and patient-level HPV vaccination initiation status (series initiated or not initiated). Participants will be assessed for eligibility and, if eligible, enrolled within the 4 clinics at their first visit time during the 12-month study period, with a total participant time on study of 13 months, for a total of 25 months of enrollment, execution, and follow-up.

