Statistical Approaches: The primary comparisons are between the rates of completing the next step in the HPV vaccination series at 6 months in the Auto, Auto-Plus, and UC arms (Primary Outcome), and between the rates of completing the HPV vaccination series at 13 months (Secondary Outcome). Completing the next step in the vaccine series and completing the vaccine series outcomes will be compared via logistic generalized estimating equations (GEE) models, 129, 130 with bias-reduced robust sandwich variance estimators 131 clustered by clinic. These logistic GEEs will be adjusted for P/C and patient features that may influence HPV vaccination series next step and completion, including age, sex, race/ethnicity, rurality, and HPV vaccination initiation status at study enrollment. Models comparing the Auto, Auto-Plus, and UC groups, will also include study arm. Comparisons between the study arms of the next-step and series-completion endpoints will be performed separately. For each endpoint, pairwise differences between arms will be assessed with a Bonferroni correction to achieve type I error control at 0.05, with p<0.017=0.05/3 needed for statistical significance. Predefined subgroup analyses will be performed by P/C and/or patient sex, age group, race/ethnicity, rurality, and HPV vaccination initiation status at study enrollment, and each of these characteristics will be assessed for effect moderation. Since next step completion and series completion will be captured via the EHR and the state-wide vaccine registry, we anticipate little missing data for these outcomes. Statistical Analysis and Power: Based on the **Table 2**, there are 1038 patients in the appropriate age range, of whom <50% will have completed the HPV vaccination series, for at least 519 patients within the eligible age range who have not yet completed the HPV vaccination series, with at least 173 in each study arm. 173 participants per study arm will ensure >80% power for detecting rate differences for both the next step endpoint and series completion endpoint exceeding 0.17, under the Bonferroni statistical significance benchmark of p<0.017. If the completion endpoint rate is 50% in the Auto-Plus arm and is 33% in the UC arm (rate difference 0.17), then the proposed study will have 80% power for detecting a difference by arm. Moderators: We will assess differences across study arms in our secondary outcome: missed opportunities, defined as patients who receive other recommended vaccinations, but not HPV. We will also explore possible moderators of effectiveness: age (11– 14, 15–17), ethnicity (Hispanic vs. non-Hispanic white), sex (male vs. female vs. other), language (Spanish vs. English), poverty status (<100% Federal Poverty Level vs ≥100% Federal Poverty Level), and insurance status (commercial vs. Medicaid vs. other). Thus, we will consider **sex a biological variable**, an important distinction because of differing rates of HPV vaccination and barriers faced by adolescent males and females. 132-135 By assessing differences in effectiveness across the life course of ages 11-14 and 15-17, we will understand differences in groups for whom 2 doses and 3 doses of the vaccine is recommended. Each potential moderator will be tested separately by considering its main effect and interaction with study arm in the logistic mixed effects models (Aim 2). Evidence of differential intervention effectiveness will be supported by an overall test of

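### C.1 and C.5.b give 1038 as the number in the trial, but 1038 is every patient aged 11–17 at the four clinics, including those who have completed the series and cannot be randomised

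*Combined protocol and SAP*

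**What the plan says.** Two sections give 1038 as the size of the randomised trial. C.1 (Project Overview): "The individual-RCT will include P/Cs of 1038 vaccine-eligible patients at 4 rural clinics in Washington". C.5.b (Intervention Process, vaccine initiation): "We will select a cohort of approximately 1,038 P/C of patients from the 4 clinics, randomized to intervention arms".

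C.5.d gives the same number a different meaning. Its Study Design paragraph limits randomisation to children with doses outstanding: "P/C of C/A who have not completed the HPV vaccination series will be randomized 1:1:1 to study arms". Its power paragraph, citing Table 2, says "there are 1038 patients in the appropriate age range, of whom <50% will have completed the HPV vaccination series", and from this derives a floor "for at least 519 patients within the eligible age range who have not yet completed the HPV vaccination series". Dividing that floor by three, it arrives at an allocation "with at least 173 in each study arm".

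Table 2 (in C.2) lists the number of patients aged 11–17 at each clinic, with completion rates for ages 11–12 and 13–17. Its footnote reads "Estimated 5% decline in HPV vaccination rates shown due to COVID-19 pandemic challenges".

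**The concern.** One number serves both as the source pool and as the cohort drawn from it. Both uses can be right only if nobody in the pool has completed the series, and Table 2 reports completers in both age bands at all four clinics.

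The planned number randomised is a core design parameter, and the plan gives two answers: 1038 in the overview and the randomisation text, and at least 519 in the power paragraph. A reader who takes 1038 as the sample size thinks the trial is larger than the one that was powered. Anyone who later compares enrolment with 1038 would see a shortfall even if the trial had met its power basis. Read literally, the C.5.b sentence could be met only by adding children who have no next dose to receive, and so cannot have the primary outcome, or by going beyond the Table 2 pool.

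**Working it through.** **Inputs.** Clinic counts and completion rates are from Table 2. The population randomised is from Study Design in C.5.d. The 519, the 173 per arm, the rates of 33% and 50%, and the threshold 0.05/3 are from the statistical paragraphs of C.5.d.

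**1. The plan's own figures.**
- Table 2 total: 158 + 241 + 73 + 566 = 1038.
- Non-completers at the 50% limit: 1038 × 0.5 = 519.
- Per arm: 519 / 3 = 173.
- Power for 33% against 50% at 173 per arm. The test is assumed two-sided at 0.05/3 (the plan does not state the side), with no allowance for clustering and z = 2.394:
  - Null standard error with pooled rate 0.415: √(2 × 0.415 × 0.585 / 173) = 0.0530.
  - Alternative standard error: √((0.33 × 0.67 + 0.50 × 0.50) / 173) = 0.0522.
  - Pooled: Φ((0.17 − 2.394 × 0.0530) / 0.0522) = 79.6%.
  - Unpooled: Φ(0.17 / 0.0522 − 2.394) = 80.6%.

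The 519, the 173 and the 80% all reproduce. The design therefore rests on 519 patients, not 1038.

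**2. How many of the 1038 could be randomised.** Non-completers = Σ N × (1 − completion rate). At every clinic the rate at 11–12 is below the rate at 13–17, so applying each rate to everyone bounds any age mix.

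| Clinic | N, 11–17 | Completed, 11–12 | Completed, 13–17 | Non-completers if all 13–17 | Non-completers if all 11–12 |
|---|---|---|---|---|---|
| Ocean Shores | 158 | 2.6% | 25.6% | 117.6 | 153.9 |
| Aberdeen | 241 | 8.5% | 44.8% | 133.0 | 220.5 |
| Elma | 73 | 16.3% | 67.7% | 23.6 | 61.1 |
| Yelm | 566 | 18.2% | 44.3% | 315.3 | 463.0 |
| Total | 1038 | | | 589.4 | 898.5 |

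Completers within the 1038 therefore number between 1038 − 898.5 = 139.5 (13%) and 1038 − 589.4 = 448.6 (43%). If ages are spread evenly over 11–17, so that 2/7 are aged 11–12 (an assumption), non-completers number (2/7) × 898.5 + (5/7) × 589.4 = 677.7.

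**3. Sensitivity to the footnote.** The printed rates include an estimated 5% decline, and the plan does not say whether it is relative or in percentage points. Undoing it raises completion and lowers the count:

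| Reading of the rates | All 13–17 | Even ages | All 11–12 |
|---|---|---|---|
| As printed | 589 | 678 | 898 |
| Relative 5% undone (rate / 0.95) | 566 | 659 | 891 |
| 5 percentage points undone (rate + 5) | 538 | 626 | 847 |

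No cell reaches 1038, and every cell is above 519. All 1038 would be eligible only with 0% completion everywhere. The lowest printed rate is 2.6%.

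**4. Size of the overstatement.**
- Printed rates: 1038 / 898.5 = 1.16 to 1038 / 589.4 = 1.76.
- Even ages, printed rates: 1038 / 677.7 = 1.53.
- Lowest reading in the table: 1038 / 537.5 = 1.93.
- Against the power basis: 1038 / 519 = 2.

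**5. Cross-check.** If 1038 were randomised (1038 / 3 = 346 per arm), power for 33% against 50% would be about 98.5%, and 80% power would be reached at a difference of about 0.12. The plan states 80% at 0.17, so 1038 is not the trial that its power paragraph describes.

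**The case against.** The strongest case is that nothing would go wrong in practice. C.5.b and C.5.c build the outreach lists from patients due for a first or a follow-up dose, C.4.b makes vaccination history part of eligibility, Study Design randomises non-completers only, and C.7 checks lists against the registry. No completer would be randomised. The paragraph that governs sample size uses the number properly, and C.5.b says approximately. This stands as far as conduct and analysis go. It does not rescue the label, because those same rules are why 1038 cannot be the number randomised. A gap of 140 to 449 patients is also more than approximately can cover.

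A second argument is that vaccine-eligible in C.1 means only eligible by age. C.4.a does use about 1038 in a setting where vaccination status is not a criterion. But C.1 says that the trial will include these patients, just after describing prompts to complete the next dose, and C.5.b says that they are randomised.

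A third is that children turning 11 during the 12-month enrolment period, or reserve clinics, could raise the number. They could, but both sentences name the four clinics, the other clinics are offered as alternates, and 1038 is nowhere derived that way. The claim is limited to the Table 2 pool.

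The last is that 519 is itself a count of available patients, before exclusions for siblings, missing contact details, language and clinical conditions. That is fair, and it is why 519 should be stated as a floor and not as an exact target. It is still the number on which the plan bases its power.

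The bounds for the overstatement are extremes of age mix, and the factor of 1.93 also requires the footnote's decline to be undone. They show the range and are not estimates.

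**Conclusion.** The concern holds. In C.1 and C.5.b, 1038 is presented as the number in the trial, but it is the count of all patients aged 11–17 at the four clinics, and C.5.d randomises only those who have not completed the series. On the printed rates, 589 to 898 of them qualify, or about 678 if ages are evenly spread. The stated size is thus 1.16 to 1.76 times the randomisable pool, and twice the power basis of 519. That some of the 1038 are ineligible needs only Table 2's non-zero completion rates. The exact size depends on the age mix, which the plan does not give, and on how the footnote's 5% is read.

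The stated trial size must be corrected, but this is not a flaw in the analysis. The power statement, the significance threshold and the planned models are unaffected.

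**What to change.** In C.1 and C.5.b, describe 1038 as the source population aged 11–17 at the four clinics. State the planned trial size in the same places as at least 519 patients who have not completed the series, at least 173 per arm, so that both sections agree with Study Design and the power paragraph in C.5.d. Keep the words at least. A projected count after sibling, contact, language and clinical exclusions would be good practice but is not needed for this correction.

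The cost is wording in two places and a smaller headline number. No extra patients are needed, and neither the power calculation nor the analysis changes.

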# C.5. Aim 2: Test a set of automated reminders (defined during Aim 1) on timely receipt of next needed HPV vaccine dose and on series completion.

We hypothesize that Auto and Auto-Plus interventions will be more effective than usual care, and Auto-Plus will be more effective than Auto at increasing receipt of the next needed HPV vaccine dose and on series completion. We will implement and evaluate the intervention in 4 clinics using an individual-RCT design (IM Steps 5 and 6). Our quantitative evaluation will assess intervention effectiveness and reach. We will gather P/C-, patient- and HCP-level data to identify possible program enhancements, as well as barriers and facilitators to adoption, implementation, and maintenance.

**C.5.a.** Convene Teams and Train Staff: Each participating clinic will convene an implementation team comprised of a clinic champion, clinic coordinator, and relevant laboratory and administrative personnel whom we will select for their ability to facilitate the intervention within the clinic settings. Once the team is formed, members of the PREVENT research team and clinic staff will train the participating clinics in delivering the intervention. Staff training will take place during a half-day session (with additional phone support) and will address procedures for identifying P/C of eligible patients and tracking automated outreach (e.g., automated phone calls, text messages). Clinics will receive training specific to the Auto-Plus components, such as the live phone call and patient navigation protocols using as computer assisted interactive system.

C.5.b. Intervention Process: Focused on HPV vaccine initiation. Through BCT, we will select a set of HPV vaccine initiation reminders to encourage uptake among age- and vaccine-eligible adolescents. Reminders could include letters (with strong provider recommendations, and bundled recommendations), text messages with links to digital stories, patient and/or P/C narratives, letters, automated phone calls, or email messages. Because we hope to implement this trial as part of standard care, our study will apply to obtain a waiver of informed consent, which was successful in STOP CRC because intervention components are similar to primary health care settings' standards of care and imply minimal risk (See Section C.2). Sea Mar analysts will create a real-time list of patients due for an initial HPV vaccine dose, and the clinic outreach coordinator will review the list and remove any patients missing telephone number or address (if a mailed intervention is selected). P/C of remaining children and adolescent patients (i.e., participants) will be individually randomized to either Auto or Auto-Plus intervention or UC, in a 1:1:1 ratio. The PREVENT study will only target one child/adolescent per parent/caregiver (siblings will be excluded from intervention assessments). In Sea Mar clinics, 87% of phone numbers of patients eligible for CRC screening (aged 50-75) could receive text messages; we expect a higher percentage for the younger cohort in this trial.88 Participant lists will be sent to Sea Mar's communications vendor (ClienTell) for delivery of automated HPV vaccine initiation prompts; the UC group will not receive tailored reminders but will only receive opportunistic vaccine reminders that are delivered during clinic visits or MyChart EHR-based patient portal reminders. As in STOP CRC, real-time participant lists will be refreshed to discontinue reminders for P/C of patients who have received a given vaccine dose.

Consistent with the desire of clinic staff to integrate this project into their standard workflows, we will use automated codes to manage interventions so that eligible patients get initial HPV vaccines on time and P/C are prompted to repeat vaccination, as recommended. Our EHR tools rely on Reporting Workbench, a population management tool in Epic which will be customized to include tools needed for tracking completion of HPV vaccination at the 4 intervention clinics. The registry will list patients' HPV vaccination history as well as key demographic variables for the intervention (e.g., name, address, preferred language). We will select a cohort of approximately 1,038 P/C of patients from the 4 clinics, randomized to intervention arms (UC, Auto, and Auto-Plus) stratified by clinic, sex, and language preference (English, Spanish, other) to ensure a nearly balanced distribution of clinic, sex, and language preference among study arms. The registry will generate 2 real-time reports: 1] HPV vaccination outcomes (i.e., date of vaccination events, and whether the event represents series initiation, second dose, and/or series completion); and 2] PREVENT intervention activities (i.e., date of

Table 3: Schedules of Measures (part.=participants; T=time, Y=year; M=month)								
Variable	Data source	How measured	Proctor/ RE- AIM domain	Т				
Aim 1: Bootcamp Translation (BCT)								
Rural parent-/ caregiver- & provider-driven adaptations/ program acceptance	Parents / providers	Notes from BCT sessions	Adaptations, Acceptance	Y 1				
Aim 2: PREVENT Randomized 0	Controlled Trial (I							
Reach of RCT – primary outcome (next needed HPV vaccine dose)	EHR; vendor logs	N part. receive program/ N anticipated, reasons	Reach	6 m				
Reach of RCT – secondary outcome (completion of HPV vaccine series)	EHR; vendor logs	N part. receive program/ N anticipated, reasons	Reach	6 m				
Effectiveness of RCT – primary outcome	EHR	N C/A complete next HPV vaccine dose/ N anticipated	Effectiveness	6 m				
Effectiveness of RCT – secondary outcome	EHR	N C/A complete all doses of HPV vaccine  / N anticipated	Effectiveness	13 m				
Aim 3: Tertiary and Qualitative	Outcomes							
Moderators (e.g., sex of parent, sex of child, age, ethnicity, etc.)	EHR data	Effectiveness of intervention by presence of moderator	Equity	6 m				
Parent/caregiver reactions	Interviews	Coded transcripts	Acceptance	Y 3				
Provider/staff reactions	Interviews	Coded transcripts	Acceptance, Adoption, Implementati on, Maintenance	Y 3				
Parent/caregiver/child EHR/Admi strative da		Delivery/receipt of interventions as intended	Fidelity	Y 3				
Clinic-, community-level barriers / facilitators to implementation/ sustainability	Interviews	Coded transcripts	Adaptations, Acceptance, Maintenance	Y 3				

mailing, date of automated phone calls, text messages, patient portal messages). We will use reports to monitor and maintain quality assurance during intervention implementation, and Reporting Workbench to automate patient-specific mass mailings for P/C, and HPV vaccine orders.

Automated Intervention (Auto): Auto intervention participants will be eligible for outreach delivered using automated phone calls, text or email messages with the mode, frequency, timing of reminders, and message content refined using BCT. Automated outreach may also include innovative communication strategies, such as text-linked videos, P/C, or patient narratives (based on BCT). Auto outreach to P/C will invite P/Cs to attend free HPV vaccination visits and will emphasize family-friendly hours.

Automated Intervention Plus (Auto-Plus): Auto-Plus intervention participants will be eligible for automated reminders, plus additional P/C prompts for patients who do not undergo vaccination within 3 weeks. These prompts may be delivered via live phone call outreach or patient navigation.

Working with clinic leadership and using the findings BCT, activities will be selected from a list of possible options from the National HPV Vaccination Roundtable (previously chaired by [name]), and our ranking of the effectiveness of language- and culturally-tailored intervention materials. Recommended interventions:

- Live phone call outreach: Live phone call outreach allows outreach staff to answer P/C questions, ease vaccination resistance, and facilitate appointment scheduling in real-time. Sea Mar outreach staff are already trained in motivational interviewing, and we prompt them in HPV-specific communication techniques (i.e., presumptive language, bundled recommendations, as appropriate).
- Interactive web-based coaching tool: Live calls will be facilitated by an interactive web-based coaching tool that prompts patient navigators during live phone calls with P/C on how to best respond to varying types and levels of P/C vaccine hesitancy. This tool will be developed by Drs. [name] and [name] in partnership with HCl's bioinformatics core. P/C identified vaccine hesitancy barriers may fall within the broad domains related to vaccine confidence, vaccine complacency, and vaccine convenience (Figure 2).
- Patient navigators: trained staff who promote healthful behaviors by addressing barriers to care. Navigators can respond to the cultural needs of their patients—such as values of *personalismo* or *respeto*. 127, 128

**C.5.c.** Intervention Process: Focused on HPV vaccine series completion. The BCT process will define the format (mode and frequency) and content of messages to promote vaccine series completion. The clinic-level analysts will generate real-time lists of patients who have initiated the HPV vaccine and are due for a follow-up dose, stratified by age group (11–14 vs. 15–17). The list will include adolescents age 11–14 years who have completed an initial dose of the HPV vaccine and are due for a second dose (within 6-12 months) and those aged 15–17 who are due for a second or third dose. While Auto and Auto-Plus interventions for series

completion may use some of the same components as vaccine initiation (automated calls, live calls, text messages, emails, and mailings), some notable differences will likely exist. HPV vaccine initiation may bundle recommendations for HPV and for other needed vaccines (e.g., "[Patient name] is due for the following vaccines: HPV; meningococcal; Tetanus, Diphtheria, Pertussis"), whereas series completion will not need bundled messages. Series completion reminders will include scheduling and appointment reminders.

**C.5.d. Evaluation:** Based on our previous research and conversation with clinic staff, we have designed Phase I to include multiple components. Using the Proctor Implementation and RE-AIM frameworks, we will track intervention reach and effectiveness. We will conduct one-on-one interviews with participants and debrief interviews with HCP to illuminate persistent barriers to HPV vaccination uptake and factors important to program acceptability, maintenance, and sustainability. **Table 3** summarizes these measures.

Program Effectiveness: We will assess intervention effectiveness for each of the three study arms, calculated as the proportion of eligible children/adolescents who received any HPV vaccine within 6 months and 13 months (series completion by one year) of randomization. We will assess the proportion of C/A who initiated HPV vaccination, those who received the next needed dose and the percent who completed the series.

Study Design: We propose a 3-arm RCT to compare rates of completing the next step in the HPV vaccination series at 6 months and completing the HPV vaccination series at 13 months between Auto, Auto-Plus, and UC arms. P/C of C/A who have not completed the HPV vaccination series will be randomized 1:1:1 to study arms, with separate randomizations within each clinic (Ocean Shores, Aberdeen, Elma, or Yelm) and patient-level HPV vaccination initiation status (series initiated or not initiated). Participants will be assessed for eligibility and, if eligible, enrolled within the 4 clinics at their first visit time during the 12-month study period, with a total participant time on study of 13 months, for a total of 25 months of enrollment, execution, and follow-up.

Statistical Approaches: The primary comparisons are between the rates of completing the next step in the HPV vaccination series at 6 months in the Auto, Auto-Plus, and UC arms (Primary Outcome), and between the rates of completing the HPV vaccination series at 13 months (Secondary Outcome). Completing the next step in the vaccine series and completing the vaccine series outcomes will be compared via logistic generalized estimating equations (GEE) models, 129, 130 with bias-reduced robust sandwich variance estimators 131 clustered by clinic. These logistic GEEs will be adjusted for P/C and patient features that may influence HPV vaccination series next step and completion, including age, sex, race/ethnicity, rurality, and HPV vaccination initiation status at study enrollment. Models comparing the Auto, Auto-Plus, and UC groups, will also include study arm. Comparisons between the study arms of the next-step and series-completion endpoints will be performed separately. For each endpoint, pairwise differences between arms will be assessed with a Bonferroni correction to achieve type I error control at 0.05, with p<0.017=0.05/3 needed for statistical significance. Predefined subgroup analyses will be performed by P/C and/or patient sex, age group, race/ethnicity, rurality, and HPV vaccination initiation status at study enrollment, and each of these characteristics will be assessed for effect moderation. Since next step completion and series completion will be captured via the EHR and the state-wide vaccine registry, we anticipate little missing data for these outcomes. Statistical Analysis and Power: Based on the **Table 2**, there are 1038 patients in the appropriate age range, of whom <50% will have completed the HPV vaccination series, for at least 519 patients within the eligible age range who have not yet completed the HPV vaccination series, with at least 173 in each study arm. 173 participants per study arm will ensure >80% power for detecting rate differences for both the next step endpoint and series completion endpoint exceeding 0.17, under the Bonferroni statistical significance benchmark of p<0.017. If the completion endpoint rate is 50% in the Auto-Plus arm and is 33% in the UC arm (rate difference 0.17), then the proposed study will have 80% power for detecting a difference by arm. Moderators: We will assess differences across study arms in our secondary outcome: missed opportunities, defined as patients who receive other recommended vaccinations, but not HPV. We will also explore possible moderators of effectiveness: age (11– 14, 15–17), ethnicity (Hispanic vs. non-Hispanic white), sex (male vs. female vs. other), language (Spanish vs. English), poverty status (<100% Federal Poverty Level vs ≥100% Federal Poverty Level), and insurance status (commercial vs. Medicaid vs. other). Thus, we will consider **sex a biological variable**, an important distinction because of differing rates of HPV vaccination and barriers faced by adolescent males and females. 132-135 By assessing differences in effectiveness across the life course of ages 11-14 and 15-17, we will understand differences in groups for whom 2 doses and 3 doses of the vaccine is recommended. Each potential moderator will be tested separately by considering its main effect and interaction with study arm in the logistic mixed effects models (Aim 2). Evidence of differential intervention effectiveness will be supported by an overall test of

the potential moderator by study arm interaction effects.

